#### 5. Sample Size and Power Considerations

This study will randomize 33 subjects (22 to Pro-ocular™ 1% topical gel, and 11 to Placebo).

#### 6. Data Preparation

All study data will be recorded on an Excel file prepared by Glia. The file contains multiple worksheets.

Diary data will be collected from subjects at the protocol specified visits and entered by Ora staff into the Excel file as well. Glia and the Ora data entry specialists will review data to ensure accuracy and cleanliness.

The data will be transferred to SDC and then converted into SAS datasets. After data are converted to SAS, limited electronic edit checks and data review will be performed to ensure data is analyzable.

This study will be locked in 2 phases. The first lock will occur after completion of the Study Treatment Phase, including all data up to Visit 5. This will constitute the Primary database lock. The second database lock will occur after completion of the Placebo Cross-over Phase, including all data up to Visit 7. This will constitute the Final database lock.

When all prerequisites for database lock have been met, including availability of all masked external data, the database will be locked. Following database lock, approval will be obtained from the Sponsor to unmask

the study. Once the study has been unmasked, unmasked data will be sent to SDC. Any changes to the database after data have been locked can only be made with the approval of the Sponsor in consultation with SDC.

The primary analysis will be carried out after the following have occurred:

- Primary Database lock has occurred, including receipt of all final versions of external vendor data, with written authorization provided by appropriate SDC and Sponsor personnel.
- Protocol deviations have been identified and status defined (major/minor deviations).
- Analysis populations have been determined.
- Randomized treatment codes have been unmasked.

The final analysis will be carried out after the following have occurred:

- Final Database lock has occurred, including receipt of all final versions of external vendor data, with written authorization provided by appropriate SDC and Sponsor personnel.

## 7. Analysis Populations

### 7.1 Modified Intent-to-Treat

The modified intent-to-treat (ITT) population includes all randomized subjects who received at least 1 application of the study drug. Subjects will be analyzed as randomized.

### 7.2 Per Protocol

The per protocol (PP) population excludes subjects from the ITT population with significant protocol deviations and any subjects with more than 10% missing data in the Glia Ocular Surface Disease Questionnaire. Protocol deviations will be assessed for inclusion by the clinical team, prior to database lock.

The subjects will be analyzed as randomized. If both treatments groups in the PP population retain  $\geq 85\%$  of the subjects from the corresponding treatment group in the ITT population, all analyses using the PP population will not be conducted.

### 7.3 Safety

All subjects who received at least 1 application of the study drug will be included in the Safety population. Subjects will be analyzed as treated.

## 8. General Statistical Considerations

### 8.1 Unit of Analysis

The unit of analysis in this study will be the worse eye at baseline for each ocular sign and symptom efficacy measurement. The other eye will be referred to as the fellow eye. Both eyes will be summarized separately unless stated otherwise. The term, eye type, will refer to worse eye and fellow eye. Additionally all eyes under active treatment will be compared to all eyes under placebo. (Combined eye.)

The eye will be the unit for analysis for safety summaries and both eyes will be summarized as Right Eye (OD) and Left Eye (OS) separately.

Non-ocular AEs, non-ocular medical history, non-ocular concomitant medications, Facial Presentation and Blinks per Minute and NIH eye score will be presented at the subject level.

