## **8.4 Data Analysis Conventions**

The Primary analysis will be performed by Statistics & Data Corporation (SDC) after the Study Treatment Phase is completed and the database has been locked and released for unmasking. An additional analysis will be completed once the Cross-over Phase is completed and the database for that portion is locked. Statistical programming and analyses will be performed using SAS® version 9.4 or higher. Output will be provided in rich text format (RTF) for tables, Excel format for tables and listings, and portable document format (PDF) for figures using landscape orientation for any PDF or RTF. All study data will be listed by subject, treatment, and visit (as applicable) based on all randomized subjects unless otherwise specified.

Summaries for continuous and ordinal variables will include the number of observations (n), arithmetic mean, standard deviation (SD), median, minimum, and maximum. Minima and maxima will be reported with the same precision as the raw values; means and medians will be presented to one additional decimal place than reported in the raw values. Standard deviations will be presented to two additional decimal places than reported in the raw values. Summaries for discrete variables will include counts and percentages. All percentages will be rounded to one decimal place (ie, XX.X%). Differences between active treatment group and placebo will be calculated as active minus placebo and change from baseline will be calculated as follow-up visit minus baseline.

All statistical tests will be two-sided with a significance level of 0.05 ( $\alpha = 0.05$ ) unless otherwise specified. Confidence intervals (CI) for differences between treatment groups will be two-sided at 95% confidence intervals. All p-values will be rounded to 4 decimal places; p-values less than 0.0001 will be presented as "<0.0001"; p-values greater than 0.9999 will be presented as ">0.9999."

Unless otherwise specified, summaries will be presented by treatment group and, where appropriate, visit. Listings will be sorted by treatment group, subject number, visit/time point, and parameter as applicable.

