#### Additional analyses:

For each symptom, an analysis of covariance (ANCOVA) will be used to compare change from baseline between Pro-ocular and placebo with adjustments for baseline symptom score (BASELINE), treatment group (TRT), visit (VISIT), eye type (EYETYPE) and treatment x visit interaction (TRT\*VISIT) as the explanatory variable. The least squares (LS) means, LS mean differences, SEs, two-sided 95% CIs for the difference in LS means, and two-sided p-values (unadjusted only) will be reported for the treatment effect at each visit and all visits combined. The model effect will also be displayed.

```
PROC MIXED data=indata order=internal;
  class TRT VISIT;
  model CFB = TRT EYETYPE BASELINE VISIT TRT*VISIT;
  LSMEANS TRT VISIT EYETYPE TRT*VISIT / CL PDIFF;
run;
```

The ITT population using only observed cases will be used for this analysis. Both ANCOVA analyses will be truncated at Visit 5 and any data presented after Visit 5 will be summarized with continuous described statistics. Continuous descriptive statistics will be used to summarize each symptom score by eye type, visit, and treatment group. Change from baseline will also be summarized. Two sample t-tests will be used to compare Pro-ocular to placebo for the visit score and for the change from baseline.

During the Study Treatment Phase, the changes from baseline will be relative to the Study Treatment Phase baseline. During the Placebo Cross-over Phase, the changes from baseline will be relative to the Placebo Cross-over Phase baseline.

Analyses will be performed on the ITT population using observed cases.

All Symptom scores will be presented in a subject listing.

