### 13.2.1 Analysis of SANDE Questionnaire

The primary and additional analyses for the modify SANDE Questionnaire will be the same as the Glia Ocular Surface Disease Symptoms Questionnaire. Both ANCOVA analyses will be truncated at Visit 5 and any data presented after Visit 5 will be summarized with continuous descripted statistics.

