### 13.5.3 Slit Lamp without Staining

Slit lamp biomicroscopy examinations without staining will be performed at Visit 1 and Visits 3 – 7. The exam will assess the following components, by eye:

- Lids (erythema, edema, lid margin ulceration, lid margin notches, entropion/ ectropion, trichiasis/madarosis, floppy eyelids, hordeolum (stye))
- Conjunctiva (hyperemia, cicatricial changes, pseudomembranes, chalasis)
- Cornea (edema, corneal ulcers, filamentous keratitis, corneal thinning, corneal neovascularization, scars, conjunctival epithelium invasion, limbal thickening)
- Anterior Chamber (cells, flare)
- Lens (status, opacity)

A VAS ranging from None to Most will be used to score each component except for Lens.

The Investigator will mark a vertical slash on the VAS to indicate the level of severity.

The result (in mm), will be measured from left endpoint to the slash marked by the Investigator on the line.

For each component, a score is derived by converting the measure length to a maximum score of 10 with one decimal place as follows:

$$\text{Score} = \text{Measured Result (mm)} * 10 / \text{CRF Scale Length (mm)}$$

The Investigator will classify any abnormal results as Abnormal Clinically Significant (CS), or Abnormal Not Clinically Significant (NCS), including any other pathologies noted by the Investigator.

The Lens status will be classified as Phakic, Pseudophakic or Aphakic. For Phakic lens, the Lens Opacity will be scored as 0, +1, +2, or +3.

All continuous slit-lamp measures will be analysed the same as Glia Ocular Surface Disease Symptoms Questionnaire and the modified SANDE Questionnaire with the following exceptions. Only the ITT populations using observed cases will be performed and no adjustments for multiplicity will be applied.

The abnormal findings will be summarized using counts and percentages for each treatment group at each visit for each eye. Percentages will be based on the number of subjects in each treatment group with responses. Shift tables will also be provided comparing each follow-up visit to baseline.

During the Study Treatment Phase, the changes (or shifts) from baseline will be relative to the Study Treatment Phase baseline. During the Placebo Cross-over Phase, the changes (or shifts) from baseline will be relative to the Placebo Cross-over Phase baseline.

Analyses will be performed on the ITT population using observed data only.

All slit lamp results will be presented in a subject listing.

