## 16. Changes from Protocol-Stated Analyses

The protocol and SAP call for LOCF imputation and for sensitivity analyses in the Per Protocol population for the key efficacy endpoints. Given there is only 1 early discontinuation and no expected major protocol deviations, the LOCF imputation and Per Protocol population have been removed due to the expected similarity with the ITT Population using only observed data. The protocol calls for t-tests and ANCOVA analyses for ordinal data, It has been decided that the Wilcoxon Rank Sum Test will be sufficient and the t-test and ANCOVA will not be done.

All crossover data collected will be summarized with continuous descriptive statistics or with counts and percentages as appropriate.

Interblink interval may appear in the protocol however all instances of interblink interval have been changed to Facial Presentation and Blinks per Minute

Per the Sponsor an additional ANCOVA model including eye type has been added for the key efficacy variables.

Additional exploratory analyses may be requested after final analyses and may be detailed in the clinical study report.

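### The combined-eye ANCOVA for clinic GLIA, SANDE and slit lamp treats a subject's two eyes as independent; at a between-eye correlation of 0.5 its per-visit type I error is about 11–12%, not 5%.

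*SAP*

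**What the plan says.** The unit of randomisation is the subject (SAP section 4.1): "This study will randomize 33 subjects (22 to Pro-ocular™ 1% topical gel, and 11 to Placebo". The gel goes on the forehead (SAP section 4), so there is no within-subject contrast between a treated and an untreated eye.

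SAP section 8.1 makes the worse eye at baseline the unit of analysis for efficacy, then adds: "Additionally all eyes under active treatment will be compared to all eyes under placebo. (Combined eye". The model for this is in section 13.1.1 under Additional analyses: "model CFB = TRT EYETYPE BASELINE VISIT TRT*VISIT", with "LSMEANS TRT VISIT EYETYPE TRT*VISIT / CL PDIFF". The prose there lists the same terms as the code. It asks for unadjusted two-sided p-values and 95% intervals at each visit and over all visits.

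Other outcomes inherit the model:

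- **SANDE (section 13.2.1):** "The primary and additional analyses for the modify SANDE Questionnaire will be the same as the Glia Ocular Surface Disease Symptoms Questionnaire".
- **Slit lamp (section 13.5.3):** "All continuous slit-lamp measures will be analysed the same as Glia Ocular Surface Disease Symptoms Questionnaire and the modified SANDE Questionnaire", on observed cases and without multiplicity adjustment.

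Section 16 records where the model came from: "Per the Sponsor an additional ANCOVA model including eye type has been added for the key efficacy variables". Section 19 lists combined-eye tables for all three outcomes. Section 8.4 sets the level: "All statistical tests will be two-sided with a significance level of 0.05".

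**The concern.** Stacking both eyes doubles the records without doubling the independent information. A fixed eye-type effect removes the mean difference between worse and fellow eye. It does nothing about the correlation between two eyes of one person, and PROC MIXED without a RANDOM or REPEATED statement treats every record as independent.

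The omission does not look like shorthand. In section 13.1.2 the diary model is said to account for repeated measures, and its code names the subject. The section 13.1.1 model does neither.

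What is at stake is how the combined-eye tables will be read. With only 11 placebo subjects, an all-eyes result with a small p-value beside the worse-eye primary could be taken as corroboration that the data do not give.

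**Working it through.** **Inputs from the documents.** 22 versus 11 subjects (SAP section 5); two eyes per subject; two-sided 0.05 (section 8.4); post-baseline Visits 3, 4 and 5. The SAP does not say whether the GLIA post-dose assessment at Visit 2 is a VISIT level, so three and four time points are both shown. The single early discontinuation mentioned in section 16 is ignored.

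**Assumed input.** The between-eye correlation of baseline-adjusted change, rho, is not in the documents. A range is used.

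**Degrees of freedom the model claims.** With three visits there are 33 × 2 × 3 = 198 records and 1 + 1 + 1 + 1 + 2 + 2 = 8 parameters (intercept, TRT, EYETYPE, BASELINE, VISIT, TRT*VISIT), so 190 residual df. With four time points: 33 × 2 × 4 = 264 records, 10 parameters, 254 df. Only 33 subjects were randomised.

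**Analytic size at one visit.** The variance of a subject's two-eye mean is σ²(1 + rho)/2; the model uses σ²/2. The treatment contrast therefore has (1 + rho) times the variance the model reports, and actual alpha = 2[1 − Φ(1.96/√(1 + rho))]. At rho = 0 this returns the plan's 5.0%. At rho = 0.5, 1.96/√1.5 = 1.60, which gives 10.95%.

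**Simulation of the written model.** Null data, 4,000 runs per cell (Monte Carlo standard error about 0.3–0.7 percentage points), least-squares fit of the SAP's terms, worse eye = higher baseline, visit correlation 0.5 on raw scores. Error at the last visit:

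| rho | Analytic | 3 visits | 4 visits |
|---|---|---|---|
| 0 | 5.0% | 5.4% | 5.4% |
| 0.2 | 7.4% | 8.0% | 7.4% |
| 0.3 | 8.6% | 9.4% | 9.1% |
| 0.5 | 11.0% | 11.7% | 11.2% |
| 0.6 | 12.1% | 12.5% | 12.6% |
| 0.8 | 14.4% | 14.6% | 15.5% |
| 0.9 | 15.5% | 16.4% | 17.0% |

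A second simulation, with the correlations placed on baseline-adjusted change, gave 11.2–12.7% per visit at rho 0.5 for visit correlations from 0 to 0.7.

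**Consequences.**

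- *Interval width.* Intervals are too narrow by √(1 + rho): 1.10, 1.22 and 1.38 at rho 0.2, 0.5 and 0.9.
- *Nominal p needed for a true 5% test.* Take t(31, 0.975) = 2.04, multiply by √(1 + rho), and refer it to the model's 190 df: 0.027, 0.013 and 0.007 at rho 0.2, 0.5 and 0.8. Referred to 64 df, as in a single-visit test on 66 eyes, the values are 0.029, 0.015 and 0.008.
- *Expected false positives at one visit.* The key outcomes are 15 GLIA symptoms and 3 SANDE scores. At 5%, 18 × 0.05 = 0.9. At rho 0.5, 18 × 0.112 to 18 × 0.117 is 2.0–2.1. At rho 0.8, 18 × 0.146 to 18 × 0.155 is 2.6–2.8.

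**All visits combined.** This test also ignores correlation between visits, a fault the single-eye primary model shares. With visit correlation 0.5 on raw scores, the combined-eye error is 14% (three visits) or 17% (four) at rho 0, and 23% or 26% at rho 0.5; the difference is the part due to pooling eyes. If 0.5 is instead the correlation of baseline-adjusted change, the figures at rho 0.5 are 27% and 31%. The conventions differ because a raw 0.5 leaves (0.5 − 0.25)/(1 − 0.25) = 0.33 after baseline adjustment.

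**Check of the remedy.** ANCOVA on the subject's two-eye mean with the subject-mean baseline gave 4.6–5.6% at the last visit in the first simulation and 4.1–5.6% in the second. The average over visits gave 4.5–5.8%. This is a complete-data stand-in; the unstructured mixed model itself was not fitted.

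**The case against.** The strongest reply is about weight. The worse eye is the unit of analysis, the hypotheses in SAP section 2.5 concern the worse eye only, and the primary model runs by eye type. Its simulated per-visit error is 5.1–5.2%. The Benjamini-Hochberg adjustment covers only the primary analysis, and no success rule uses the combined-eye p-values. The protocol's Efficacy Analyses section treats test results as additional descriptors. All of this stands, and it limits the consequence. It does not make the reported intervals and p-values right.

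The second reply is that rho is unknown. Eligibility requires disease in at least one eye, so asymmetric disease is possible and 0.5 may be too high. That is fair: 11–12% is conditional on 0.5. But error exceeds 5% at every positive value, and two eyes sharing one person, one systemic disease and one treatment are unlikely to be uncorrelated.

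Third, many slit-lamp components may be scored mostly at None, and the table above describes roughly continuous scores. This stands as a limit on the figure: a check with censored scores gave about 8%, smaller but still above 5%.

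Fourth, pooling eyes is legitimate with a suitable covariance, so section 8.1 alone is not wrong. Agreed. The fault is in the section 13.1.1 model that carries it out.

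**Conclusion.** The concern holds. As written, the combined-eye ANCOVA for clinic GLIA, SANDE and continuous slit-lamp measures gives intervals that are too narrow and p-values that are too small at any positive between-eye correlation. For roughly continuous scores, per-visit type I error is 7–8% at rho 0.2, 11–12% at 0.5 and 15–16% at 0.8. These figures rest on an assumed rho, complete data and a simple covariance. The structural fault does not depend on them.

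The finding does not reach the worse-eye hypotheses, the primary model's per-visit tests, or the diary model as written, which has a subject term. For fluorescein staining the SAP gives only t-tests and a combined-eye table title, so how its two eyes would be handled is not stated. This should be fixed before the combined-eye tables are produced or cited as support.

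**What to change.** For each combined-eye analysis of clinic GLIA, SANDE and slit lamp, use the mean of the two eyes per subject and visit. Adjust for the subject-mean baseline and specify REPEATED VISIT / SUBJECT=SUBJ TYPE=UN with DDFM=KR. This also deals with the visit correlation in the all-visits comparison of these tables.

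If both eyes are to be kept as records, specify a subject-level covariance over eye and visit, for example TYPE=UN@UN, with SUBJ and EYETYPE in CLASS. As a direct product, that structure sets the between-eye correlation across visits to the eye correlation times the visit correlation, so the SAP should state this assumption. In any case the current code needs correcting: EYETYPE is requested in LSMEANS but is missing from CLASS.

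For the combined-eye staining and diary tables, state that any test uses one value per subject or a subject-level covariance, and that t-tests will not be run on pooled eyes.

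The cost is SAP wording and a few lines of code. No data are lost. Intervals will be wider and p-values larger in the combined-eye tables.

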## **8.2 Missing or Inconclusive Data Handling**

There will be no imputation for missing data.

## **8.3 Definition of Baseline**

For the Study Treatment Phase, baseline is defined as the last measurement prior to the first dose of study medication.

For the Cross-over Phase, baseline is defined as the last measurement prior to the first dose of Pro-ocular™ 1% topical gel, which is expected to start on the day after Visit 5.

## **8.4 Data Analysis Conventions**

The Primary analysis will be performed by Statistics & Data Corporation (SDC) after the Study Treatment Phase is completed and the database has been locked and released for unmasking. An additional analysis will be completed once the Cross-over Phase is completed and the database for that portion is locked. Statistical programming and analyses will be performed using SAS® version 9.4 or higher. Output will be provided in rich text format (RTF) for tables, Excel format for tables and listings, and portable document format (PDF) for figures using landscape orientation for any PDF or RTF. All study data will be listed by subject, treatment, and visit (as applicable) based on all randomized subjects unless otherwise specified.

Summaries for continuous and ordinal variables will include the number of observations (n), arithmetic mean, standard deviation (SD), median, minimum, and maximum. Minima and maxima will be reported with the same precision as the raw values; means and medians will be presented to one additional decimal place than reported in the raw values. Standard deviations will be presented to two additional decimal places than reported in the raw values. Summaries for discrete variables will include counts and percentages. All percentages will be rounded to one decimal place (ie, XX.X%). Differences between active treatment group and placebo will be calculated as active minus placebo and change from baseline will be calculated as follow-up visit minus baseline.

All statistical tests will be two-sided with a significance level of 0.05 ( $\alpha = 0.05$ ) unless otherwise specified. Confidence intervals (CI) for differences between treatment groups will be two-sided at 95% confidence intervals. All p-values will be rounded to 4 decimal places; p-values less than 0.0001 will be presented as "<0.0001"; p-values greater than 0.9999 will be presented as ">0.9999."

Unless otherwise specified, summaries will be presented by treatment group and, where appropriate, visit. Listings will be sorted by treatment group, subject number, visit/time point, and parameter as applicable.

### 8.5 Adjustments for Multiplicity

The Benjamini-Hochberg procedure will be used to adjust for multiplicity for the primary analysis of the key efficacy variables.

The Benjamini-Hochberg procedure is as follows:

- 1) Sort the original p-values from smallest to largest
- 2) Assign ranks to the original p-values smallest to largest
- 3) Calculate the p-values' adjusted Benjamini-Hochberg critical value as follows:

Adjusted critical p-value = (rank of original p-value/ number of tests i.e. largest rank)\*false discovery rate, or  $\alpha = 0.05$ .

- 4) Compare the original p-values to adjusted critical p-values; find the largest original p-value that is  $\leq 0.05$ ;
- 5) Reject the null for any original p-values that is the largest original p-value in 4) or smaller than the p-value in 4).

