## 1. Introduction

The purpose of this statistical analysis plan (SAP) is to describe the planned analyses and reporting for protocol oGvHD-1, version 4.0 dated 07APR2019.

This SAP is being written with due consideration of the recommendations outlined in the most recent International Conference on Harmonisation (ICH) E9 Guideline entitled Guidance for Industry: Statistical Principles for Clinical Trials and the most recent ICH E3 Guideline, entitled Guidance for Industry: Structure and Content of Clinical Study Reports.

This SAP describes the data that will be analyzed and the subject characteristics, efficacy, and safety assessments that will be evaluated. This SAP provides details of the specific statistical methods that will be used. The statistical analysis methods presented in this document will supersede the statistical analysis methods described in the clinical protocol. If additional analyses are required to supplement the planned analyses described in this SAP, they may be completed and will be identified in the clinical study report.

The planned analyses include:

1. The Primary analysis of the Study Treatment Phase will occur after all subjects have completed or discontinued through Visit 5.
2. The final/secondary analysis of the Cross-over Phase will occur after all subjects who enter the Cross-over Phase have completed or discontinued through Visit 7.

This SAP will be finalized and signed prior to the database lock for the primary analysis.

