### 2.5 Statistical Hypotheses

The null and alternative hypotheses, based on the primary variables, are as follows:

$H_0$ : There is no difference between Pro-ocular™ 1% topical gel and placebo in the change from baseline in ocular symptom scores based on the GLIA Ocular Surface Disease Questionnaire when comparing the worse eye for each symptom.

$H_a$ : The change from baseline in ocular symptom scores based on the GLIA Ocular Surface Disease Questionnaire is larger with Pro-ocular™ 1% topical gel than with placebo when comparing the worse eye for each symptom.

H02: There is no difference between Pro-ocular™ 1% topical gel and placebo in the change from baseline in ocular symptom scores based on the modified SANDE Questionnaire when comparing the worse eye for each symptom.

Ha2: The change from baseline in ocular symptom scores based on the modified SANDE Questionnaire is larger with Pro-ocular™ 1% topical gel than with placebo when comparing the worse eye for each symptom.

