### 13.1.1 ANALYSIS OF GLIA OCULAR SURFACE DISEASE SYMPTOMS QUESTIONNAIRE COLLECTED IN CLINIC

#### The primary analysis (Study Treatment Phase):

For each symptom, an analysis of covariance (ANCOVA) will be used to compare change from baseline between Pro-ocular and placebo with adjustments for baseline symptom score (BASELINE), treatment group (TRT), visit (VISIT), and treatment x visit interaction (TRT\*VISIT) as the explanatory variable. The least squares (LS) means, LS mean differences, SEs, two-sided 95% CIs for the difference in LS means, and two-sided p-values (unadjusted and Benjamini-Hochberg adjusted p-values) will be reported for the treatment effect at each visit and all visits combined. Model effects will also be displayed.

SAS pseudo-code for this model follows:

```
PROC MIXED data=indata order=internal;
  By EYETYPE;
  class TRT VISIT;
  model CFB = TRT BASELINE VISIT TRT*VISIT;
  LSMEANS TRT VISIT TRT*VISIT / CL PDIFF;
run;
```

The ITT population will be used as the primary population using LOCF for imputation.

Sensitivity analyses will include the ITT population and PP population using observed cases.

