### **13.2 Modified SANDE – Symptom Assessment iN Dry Eye Questionnaire**

The Modified SANDE – Symptom Assessment iN Dry Eye Questionnaire will be collected at Visit 1 and Visits 3 – 7.

A VAS will be used to assess subject's symptoms, by eye, for the following:

- Frequency of Symptoms
- Severity of Symptoms

First, the subject will be asked to place a vertical line to indicate how often, on average, their eyes feel dry and/or irritated. For frequency, the VAS ranges from Rarely to All the Time.

Second, the subject will be asked to place a vertical line to indicate how severe, on average, they feel their symptoms of dryness and/or irritation are. For severity, the VAS ranges from Very Mild to Very Severe.

The result (in mm) will be measured from the left endpoint to the slash marked by subject on the line.

For each symptom, a score is derived by converting the measure length to a maximum score of 100 with one decimal place as follows:

$$\text{Score} = \text{Measured Result (mm)} * 100 / \text{CRF Scale Length (mm)}$$

The total SANDE score is calculated by multiplying the frequency of symptoms score with the severity of symptoms score and obtaining the square root.

Subjects whose values are all 0 for a given symptom for all visits will not be included in the analysis for that symptom

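### Step 4 of the SAP's Benjamini-Hochberg procedure uses a fixed cut-off of 0.05 instead of each p-value's own critical value, so as written it adjusts nothing

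*SAP*

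**What the plan says.** SAP section 8.5 applies the Benjamini-Hochberg procedure to the primary analysis of the key efficacy variables, which section 2.2 lists as the clinic GLIA questionnaire and the modified SANDE. After ranking the p-values, the section proceeds as follows:

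- Step 3: "Adjusted critical p-value = (rank of original p-value/ number of tests i.e. largest rank"), multiplied by 0.05.
- Step 4: "Compare the original p-values to adjusted critical p-values; find the largest original p-value that is" ≤ 0.05.
- Step 5: "Reject the null for any original p-values that is the largest original p-value in 4) or smaller than the p-value in 4").

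Section 13.1.1 fits a model to each of the 15 GLIA symptoms. It says that two-sided p-values ("unadjusted and Benjamini-Hochberg adjusted p-values) will be reported for the treatment effect at each visit and all visits combined". Section 13.2.1 carries this over: "The primary and additional analyses for the modify SANDE Questionnaire will be the same as the Glia Ocular Surface Disease Symptoms Questionnaire". SANDE yields frequency and severity scores and a third, derived one: "The total SANDE score is calculated by multiplying the frequency of symptoms score with the severity of symptoms score", followed by a square root. The hypotheses in section 2.5 are framed "when comparing the worse eye for each symptom".

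**The concern.** The first half of step 4 points to the rank-based critical values, but its selection clause uses a fixed 0.05. That figure equals the critical value only at the last rank. Since step 5 acts on whatever step 4 selects, the critical values from step 3 never affect a decision.

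The trial has no single primary endpoint. Section 8.5 is the only multiplicity control for 15 symptoms plus SANDE, and it decides which of them are called significant. The two readings can give different lists from the same data. A symptom could be rejected under section 8.5 while its adjusted p-value in the section 13.1.1 table is above 0.05.

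The divisor in step 3 is also undefined. No section says whether the visit contrasts and the all-visits contrast belong to one family, or whether GLIA and SANDE are pooled.

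**Working it through.** **Inputs.** From the SAP: false discovery rate 0.05 (8.5), two-sided tests (8.4), 15 GLIA symptoms (13.1), three SANDE scores (13.2). Assumed, because the SAP does not give it: m = 15 (GLIA only) or m = 18 (GLIA and SANDE pooled, one contrast each, worse eye).

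**The two rules, with p-values sorted as p(1) ≤ … ≤ p(m).**

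- As written: find the largest p(i) ≤ 0.05; reject it and all smaller ones. This is the set of all p ≤ 0.05.
- Benjamini-Hochberg: find the largest p(i) ≤ (i/m) × 0.05; reject it and all smaller ones.

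**The plan's own figure.** With all null hypotheses true and independent tests, the correct rule gives a simulated false discovery rate of 0.0498 (m = 15) and 0.0500 (m = 18), which reproduces the stated 0.05. The rule as written gives 1 − 0.95^15 = 0.537 and 1 − 0.95^18 = 0.603. In 100,000 simulated trials per setting, it rejected exactly the tests with unadjusted p ≤ 0.05 every time.

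**Correlated symptoms.** m = 18, equicorrelated normal statistics, 100,000 runs. The false discovery rate columns assume three true effects with a shift of 2.8 standard errors.

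| Correlation | Any false claim, all null: as written | Any false claim, all null: correct | False discovery rate, 3 true effects: as written | False discovery rate, 3 true effects: correct |
|---|---|---|---|---|
| 0 | 0.60 | 0.05 | 0.20 | 0.04 |
| 0.5 | 0.40 | 0.04 | 0.17 | 0.04 |
| 0.7 | 0.28 | 0.03 | 0.15 | 0.03 |
| 0.8 | 0.22 | 0.03 | 0.13 | 0.03 |

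**Example, m = 18.** Raw p-values 0.03 and 0.04, all others above 0.05. The written steps reject two. The critical values are 1/18 × 0.05 = 0.0028 and 2/18 × 0.05 = 0.0056, and no later rank can qualify because no critical value exceeds 0.05. The correct rule rejects none.

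**Conflict with the section 13.1.1 tables, m = 15.** Take p = 0.004, 0.012, 0.019, 0.028, 0.035, 0.041, 0.047, 0.09, 0.15, 0.22, 0.31, 0.44, 0.58, 0.72, 0.90. The written steps reject seven. The adjusted p-value is the minimum over j ≥ i of m × p(j)/j:

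- rank 1: 15 × 0.004/1 = 0.060
- rank 2: 15 × 0.012/2 = 0.090
- rank 3: 15 × 0.019/3 = 0.095
- ranks 4 to 7: 15 × 0.047/7 = 0.101

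All seven exceed 0.05, so the table would contradict the stated rejections.

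**Dependence on the family.** The smallest critical value is 0.05/m:

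| Family (assumed) | m | Smallest critical value |
|---|---|---|
| SANDE scores alone | 3 | 0.0167 |
| GLIA symptoms alone | 15 | 0.0033 |
| GLIA and SANDE pooled | 18 | 0.0028 |
| Pooled, over Visits 3, 4, 5 and all visits combined | 18 × 4 = 72 | 0.0007 |
| As above, plus GLIA post-dose at Visit 2, both eye types | (15 × 5 + 3 × 4) × 2 = 174 | 0.0003 |

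**The case against.** The intent is almost certainly the standard procedure. The SAP names it, defines its critical values and opens step 4 by comparing p-values with them. It also treats adjusted and unadjusted testing as different things elsewhere: the additional model in section 13.1.1 reports unadjusted p-values only, and section 13.5.3 waives adjustment for slit lamp. Standard software producing the adjusted p-values for section 13.1.1 would lead to the right decisions, and readers would see both sets. The inflation figures therefore describe what happens only if step 4 is followed literally. The 0.60 is too high for this trial in any case, because the symptoms come from the same subjects and the SANDE total is computed from the other two scores. The trial is a phase 2 study of 33 subjects with no power claim, and the protocol's Efficacy Analyses section treats test results as further description of the data. The undefined family is arguably a separate gap.

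Much of this stands. A drafting slip is the likely cause, the correlated figures are the relevant ones, and the exploratory setting limits the harm. It does not remove the error. Section 8.5 holds the only rejection rule in either document, and that rule is wrong as written. Section 1 says the SAP's methods supersede the protocol's, and section 2.5 states formal hypotheses. The documents narrow the family to the key efficacy variables but do not settle it: section 2.5 states separate GLIA and SANDE hypotheses for the worse eye, while the section 13.1.1 model is run for each eye type.

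**Conclusion.** The point holds. Steps 4 and 5 of section 8.5 amount to unadjusted testing at 0.05 and do not deliver the stated false discovery rate. With 18 tests assumed and correlations of 0.5 to 0.8, the chance of at least one false claim under the complete null is 0.40 to 0.22, against 0.04 to 0.03 for the correct procedure. With three assumed true effects, the false discovery rate at those correlations is 0.17 to 0.13, against the stated 0.05. The sizes depend on the assumed number of tests, correlation and effects; the contradiction in the text depends on none of them. This should be fixed, but it does not undermine the design. The missing family definition is a lesser, related gap: even a corrected step 4 cannot be applied reproducibly without the number of tests.

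**What to change.** Reword step 4 to select the largest original p-value that is less than or equal to its own adjusted critical p-value from step 3. Equivalently, reject wherever the Benjamini-Hochberg adjusted p-value is at most 0.05. Step 5 can stay.

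In the same edit, add one sentence naming the family: which visits, whether the all-visits contrast is included, whether GLIA and SANDE are pooled or handled separately, and which eye. The worse eye would match section 2.5. The choice is the sponsor's, but it must be fixed before results are seen. Section 1 provides the moment: "This SAP will be finalized and signed prior to the database lock for the primary analysis".

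The cost is one clause and one sentence. Fewer symptoms may be declared significant than under the literal steps. In the assumed scenario of three true effects among 18, the chance of detecting each is 0.80 as written and 0.51 under the correct rule. That difference is the price of the error control the SAP already promises, so it is no loss against a plan that meant the standard procedure.
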